5.6 Definition of Regimen Limiting Toxicities (RLT) and Suspension of Enrollment

5.6.1 Definition of RLT

Toxicity will be determined using the revised NCI Common Toxicity Criteria version 5.0 for Toxicity and Adverse Event Reporting (CTCAE) (http://ctep.info.nin.gov).

Management and dose modifications associated with the above adverse events are outlined in Section 5.7.

Participants will be observed for regimen limiting toxicity (RLT) throughout the study. The following are considered to be RLTs if they are judged possibly, probably or definitely associated with treatment. Should they occur, individual participants will be taken off study and no further injections will be given.

- Grade 2 or more any infusion reaction except for Grade 2 pain
- Grade 2 or more cytokine release syndrome
- Grade 2 or more bronchospasm or generalized uticaria (hypersensitivity)
- Grade 2 or more allergic reaction, such as exfoliative erythroderma, anaphylaxis, or vascular collapse
- Grade 2 or more autoimmune disease (e.g. hypothyroidism, autoimmune encephalitis)
- Any Grade 3 or more toxicity possibly, probably, or definitely related to the vaccine or Varlilumab with particular attention to the following events.

The following are also considered RLTs:

- Dosing delays > 6 weeks for IMA950+poly-ICLC vaccines or varillumab (Arm 1 patients only) administration.
- Delay of the scheduled surgical resection for longer than 2 weeks possibly, probably or definitely related to toxicity of the study treatment.

The following are NOT considered RLTs:

- Grade 3 nausea, vomiting, or diarrhea that resolves to ≤ grade 1 with or without treatment within 48 hours
- Grade 3 flu-like symptoms that resolve within 24 hours with the use of acetaminophen 650-1000 mg or with any NSAID

5.6.2 Events Which Will Temporarily Halt Enrollment at Any Time:

Certain events will be considered unacceptable and a single occurrence will lead to temporary closure of enrollment while under review for attribution to study therapy (not related to surgical procedures):

- The occurrence of grade 3 or 4 toxicity, excluding local skin reaction and flu-like symptoms in 3 patients
- Toxicity requiring the use of pressors, including grade 4 vascular leak syndrome or grade 3 and 4 hypotension
- Toxicity requiring ventilation support, including grade 4 respiratory toxicity

12 April 2020 Page 38 of 88 confidential

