5.7 Drug Administration Delay, Dose Reduction, and/or Discontinuation (Individual Patients)

5.7.1 Delay in treatment administration

Treatment will be delayed by 1 week if on the day of the planned vaccination

- Patient has a fever of > 101°F (38.3 °C)
- Treatment related side effects have not resolved to grade 1 or better (except for grade 2 lymphopenia and injection site reactions from prior IMA950+poly-ICLC vaccine).

If the continued inflammatory reactions at the injection site remain too severe in both legs to allow subsequent vaccines, the treatment will be suspended for up to 6 weeks from the originally scheduled date for the next vaccine. When the therapy is resumed after a delayed dose, subsequent schedules will be slid back to keep the original intervals. If the situation does not resolve in 6 weeks, this is considered RLT and the patient will be withdrawn from the protocol.

Vaccination will be held for any \geq Grade 2 non-RLT AE (except grade 2 lymphopenia or flu-like symptoms), felt to be related to therapy, until they return to \leq Grade 1.

Possible adverse events by IMA950-poly-ICLC vaccines and varillumab are summarized in Section 5.8. In circumstances where assessment of an adverse event is limited, such as by intercurrent illness, or when laboratory studies are required to assess for other causes of toxicity, the treatment schedule may be interrupted for up to 6 weeks. Delay of one vaccine (and varillumab if scheduled) administration by up to 6 weeks will not be considered a protocol violation if due to an adverse event, regardless of attribution. If one or more treatment cycle is delayed by longer than 6 weeks due to an adverse event, regardless of attribution, treatment must be discontinued.

In the case of hepatic enzyme elevation >4x baseline (which is Grade 2; 3-5 x ULN), or any other unforeseen intolerable side effects of grade 2 (except for flu-like symptoms) or greater but not meeting the RLT criteria in Section 5.3.1, IMA950-poly-ICLC vaccine will be discontinued until that toxicity has reduced to Grade 1 or less. If the vaccine cannot be reinitiated in 6 weeks, the participant will be withdrawn for the RLT.

In the pre-surgical phase:

 If the scheduled craniotomy is delayed longer than 2 weeks secondary to RLT, the patient will be withdrawn from the protocol

12 April 2020 Page 39 of 88 confidential

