• If the scheduled craniotomy is delayed for reasons not related to toxicities, i.e. related to surgical scheduling issues or patient preference, patients will still be eligible if surgery is performed ≤ 35 days from randomization AND ≤ 4 days from last vaccine.

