5.7.3 Discontinuation of the regimen

Vaccine administration will be discontinued in the following situations:

- o An RLT is observed
- o If there is a delay of scheduled craniotomy greater than 2 weeks
- If there is a delay of vaccine dosing greater than 6 weeks due to treatment related toxicity or regimen-limiting toxicity (RLT)

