9.1 Primary Objectives

9.1.1 Safety

We will determine whether it is safe to administer pre-surgical IMA950+poly-ICLC in combination with varlilumab in patients with WHO grade 2 gliomas in whom surgical resection of tumor is clinically indicated.

Endpoints will therefore include incidence and severity of adverse events, using standard criteria as well as close clinical follow-up as would be performed normally in this group of participants following vaccinations. All reported or observed toxicities and adverse events at all clinic visits will be graded, documented and reported according to a standard toxicity table, the Common Terminology Criteria for Adverse Events (CTCAE) version 5.0 (http://ctep.cancer.gov/protocolDevelopment/electronic_applications/ctc.htm#ctc_40). We will consider the regimen is unacceptably toxic if the >33% of patients develop RLT (see Section 5.6). A participant who receives the scheduled pre-surgical vaccines, surgical resection and whose tumor is found to be WHO grade II glioma will not be replaced. If the scheduled surgery is delayed longer than 2 weeks for a toxicity or any vaccine dose is delayed for 5 weeks or longer for any reason, those patients are considered to have gone off-study due to RLT even if the toxicities/AEs do not meet the criteria of RLT defined in Section 5.3.1.

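### The dosing-delay RLT rule differs between sections 5.6.1, 5.7 and 9.1.1, so a patient delayed 5 to 6 weeks resumes vaccine under one rule and is an off-study RLT under another

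*Combined protocol and SAP*

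**What the plan says.** **Section 5.6.1** has a first list of events that are RLTs only if at least possibly associated with treatment. A second list, of further RLTs, opens with "Dosing delays > 6 weeks for IMA950+poly-ICLC vaccines or" varlilumab, and no cause is required. The next bullet in that second list does carry a condition: "Delay of the scheduled surgical resection for longer than 2 weeks possibly, probably or definitely related to toxicity of the study treatment".

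**Section 9.1.1** adds that if "any vaccine dose is delayed for 5 weeks or longer for any reason, those patients are considered to have gone off-study due to RLT", even where the toxicities do not meet the RLT criteria. The same sentence counts a surgery delay of more than 2 weeks only when it is for a toxicity.

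**Section 5.7.1** works to 6 weeks.
- Where an adverse event is hard to assess, "the treatment schedule may be interrupted for up to 6 weeks".
- Delay of one administration "by up to 6 weeks will not be considered a protocol violation if due to an adverse event, regardless of attribution".
- Beyond 6 weeks for an adverse event of any attribution, treatment must be discontinued; that sentence does not use the word RLT.
- The RLT label appears where toxicity has not resolved. For injection-site reactions: "If the situation does not resolve in 6 weeks, this is considered RLT and the patient will be withdrawn from the protocol". A later sentence does the same for toxicity that prevents restarting vaccine within 6 weeks.
- Non-toxic surgery delay has its own rule, which begins "If the scheduled craniotomy is delayed for reasons not related to toxicities, i.e. related to surgical scheduling issues or patient preference" and lets such patients stay eligible within set limits.

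**Section 5.7.3** lists a vaccine delay of more than 6 weeks as a ground for discontinuation only when it is due to treatment-related toxicity or RLT.

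**Section 12.1.1** reports the RLT proportion per arm with exact 95% intervals and compares arms by Fisher's exact test. It cites section 5.3.1 for the definition, as do 5.7.1 and 9.1.1. There is no section 5.3.1; section 5.3 is Drug Administration. **Section 12.2** halts the trial on the RLT count in either arm and gives no definition of its own.

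**The concern.** One event can be classified in different ways depending on the section that the site or the analyst applies. This affects two things.

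The first is treatment. A patient whose delay ends between 5 and 6 weeks restarts vaccine under 5.7.1 and leaves the study under 9.1.1.

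The second is the endpoint. The RLT proportion is one of the two co-primary results and the sole input to the 12.2 rule. Taken literally, 5.6.1 and 9.1.1 put delays with no toxic cause into a quantity that is judged against a toxicity ceiling of 0.33. The RLT count also governs the lead-in in 4.1, but the staggering there looks only to six weeks after surgery, so long post-surgery dosing delays have little room to enter it.

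**Working it through.** **1. The sections side by side.** Assume in each case that no other RLT criterion is met.

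| Delay | 5.6.1 | 5.7.1 / 5.7.3 | 9.1.1 |
|---|---|---|---|
| Injection-site reaction, resolves at 5.5 weeks | not RLT | resumes, schedule moved back | RLT, off study |
| Unrelated adverse event, 5.5 weeks | not RLT | permitted | RLT, off study |
| Unrelated adverse event, 7 weeks | RLT | discontinued; RLT label not stated | RLT, off study |
| Injection-site reaction, unresolved beyond 6 weeks | RLT | RLT, withdrawn | RLT, off study |

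The first two rows contradict each other outright. In the third, 5.7.1 is silent on the label. The fourth agrees.

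**2. The plan's own boundary.** Inputs from 12.2: prior Beta(0.09, 1.71), with mean 0.09/1.80 = 0.05; stop when P(pRLT > 0.33) > 0.33. For n patients, the boundary is the smallest r for which P(p > 0.33) under Beta(0.09 + r, 1.71 + n − r) exceeds 0.33. At n = 5, r = 1 gives 0.116 and r = 2 gives 0.409, so the boundary is 2. At n = 6, r = 2 gives 0.312 and r = 3 gives 0.627, so it is 3. All 13 printed entries reproduce (2 at n = 3–5, 3 at 6–9, 4 at 10–12, 5 at 13–15).

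**3. Effect on the proportion.** With 15 per arm (12.1.2), one patient classified the other way moves the proportion by 1/15 = 6.7 points. Exact 95% intervals: 0/15, 0–21.8%; 1/15 = 6.7%, 0.2–31.9%; 2/15 = 13.3%, 1.7–40.5%. This step needs no assumed rate.

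**4. Effect on stopping.** The documents give no rate of unrelated long delays, so q below is an assumption. Take true pRLT as 0.05, the expected value in 12.2, and suppose that it excludes delay RLTs. The counted probability is 1 − (1 − 0.05)(1 − q): 5.0%, 6.0%, 6.9% and 9.8% for q = 0, 1%, 2% and 5%. Per-arm stopping probability P comes from an exact recursion over n = 1 to 15 with the printed boundary. Either arm is 1 − (1 − P)², with independent arms and equal rates.

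| q (assumed) | One arm, all exposed | Either arm, all exposed | Either arm, first 3 per arm unexposed | Same, and delays enter the count 3 patients later |
|---|---|---|---|---|
| 0 | 2.6% | 5.2% | 5.2% | 5.2% |
| 1% | 3.7% | 7.3% | 6.2% | 5.5% |
| 2% | 5.0% | 9.8% | 7.4% | 5.8% |
| 5% | 10.1% | 19.1% | 11.7% | 7.2% |

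Example, q = 1%, all exposed: 1 − (1 − 0.0374)² = 0.073.

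**5. Would a different prior absorb it?** Keeping the prior weight at 1.8, prior means of 6% and 7% give the printed boundary at every n. A mean of 10% changes only n = 6, from 3 to 2. The boundary is not the problem; what is counted against it is.

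**The case against.** The best defence is that counting delays of any cause is deliberate. Section 5.6.1 puts delays in a separate list, and 9.1.1 sets a toxicity condition on surgery delay and none on vaccine delay within one sentence. In an open-label trial, an any-cause rule removes discretion over attribution. This stands as a possible reason for the missing condition. It cannot explain two thresholds, or why 5.7.1 lets a patient resume whom 9.1.1 removes.

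Other points also hold, and each limits a stronger reading.
- A reader might infer that 5.7.1 flatly contradicts 5.6.1 on unrelated delays beyond 6 weeks. It does not: 5.7.1 manages treatment, and discontinuation is compatible with an RLT label. That part rests on silence. Likewise, a delay that is no protocol violation could still be an RLT.
- A reader might infer that the analysis has no usable definition. The 5.3.1 reference is stale, but only 5.6.1 is titled as the definition, and 9.1.1 itself points to section 5.6. The natural reading is that more than 6 weeks is counted and 9.1.1 is the outlier.
- A reader might make much of the upper limit passing 33% between 1/15 and 2/15. No rule uses that limit. Section 9.1.1 refers to the share of patients with RLT, 12.2 uses the count, and 2 is far below the boundary of 5 at n = 15.
- Long non-toxic delays may be rare. Section 6 gives a one-week rescheduling window, and 5.10 offers other routes off treatment. The interruption that 5.7.1 allows when it mentions intercurrent illness concerns work-up of an adverse event, not unrelated illness in general.

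**Conclusion.** The dosing-delay rule is inconsistent as written. The firm contradiction is the 5-to-6-week band, where 5.7.1 and 9.1.1 give opposite instructions about the same patient. In addition, the literal text of 5.6.1 and 9.1.1 admits non-toxic delays to the co-primary proportion and the stopping count, and nothing in 12.1.1 or 12.2 takes them out.

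The certain effect is 6.7 points on an arm's proportion per reclassified patient. The effect on stopping rests on an assumed delay rate and on reading the expected 0.05 as free of delay RLTs. From a base of 5.2%, either-arm stopping is 5.5–9.8% at rates of 1–2%, depending on exposure and recognition. It becomes material only from about 5% with prompt recognition.

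A reader might infer that the trial is likely to stop wrongly, or that the comparison of arms is biased. The documents support neither: they give no delay rate, and nothing shows that unrelated delays would differ by arm. The error is conservative and hides no harm. Severity is minor to moderate, and it is worth correcting because a co-primary endpoint should have one definition.

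**What to change.** 1. Use one threshold, more than 6 weeks, in 5.6.1, 5.7.1 and 9.1.1.
2. Attach to the dosing-delay bullet in 5.6.1 and to the delay clause in 9.1.1 the relatedness condition that the surgery-delay bullet already carries. This matches 5.7.3.
3. Correct the 5.3.1 references in 5.7.1, 9.1.1 and 12.1.1 to 5.6.1, and say in 12.2 that this definition is the one counted.
4. Tabulate unrelated long delays by arm. Give the any-cause count as a supplementary line outside the stopping rule.

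A patient with an unrelated long delay can still be taken off treatment; only the RLT label changes.

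The cost is a few words. For patients taken off study no new data field is needed, because 4.2 already requires the reason for removal to be recorded. The downside is that attribution of a delay becomes an open-label judgement, as it already is for the treatment-related RLT items, and the count becomes slightly less conservative. The supplementary any-cause line keeps that visible. If the sponsor prefers any-cause counting on purpose, the plan should say so and still use one threshold throughout.

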5.7 Drug Administration Delay, Dose Reduction, and/or Discontinuation (Individual Patients)

5.7.1 Delay in treatment administration

Treatment will be delayed by 1 week if on the day of the planned vaccination

- Patient has a fever of > 101°F (38.3 °C)
- Treatment related side effects have not resolved to grade 1 or better (except for grade 2 lymphopenia and injection site reactions from prior IMA950+poly-ICLC vaccine).

If the continued inflammatory reactions at the injection site remain too severe in both legs to allow subsequent vaccines, the treatment will be suspended for up to 6 weeks from the originally scheduled date for the next vaccine. When the therapy is resumed after a delayed dose, subsequent schedules will be slid back to keep the original intervals. If the situation does not resolve in 6 weeks, this is considered RLT and the patient will be withdrawn from the protocol.

Vaccination will be held for any \geq Grade 2 non-RLT AE (except grade 2 lymphopenia or flu-like symptoms), felt to be related to therapy, until they return to \leq Grade 1.

Possible adverse events by IMA950-poly-ICLC vaccines and varillumab are summarized in Section 5.8. In circumstances where assessment of an adverse event is limited, such as by intercurrent illness, or when laboratory studies are required to assess for other causes of toxicity, the treatment schedule may be interrupted for up to 6 weeks. Delay of one vaccine (and varillumab if scheduled) administration by up to 6 weeks will not be considered a protocol violation if due to an adverse event, regardless of attribution. If one or more treatment cycle is delayed by longer than 6 weeks due to an adverse event, regardless of attribution, treatment must be discontinued.

In the case of hepatic enzyme elevation >4x baseline (which is Grade 2; 3-5 x ULN), or any other unforeseen intolerable side effects of grade 2 (except for flu-like symptoms) or greater but not meeting the RLT criteria in Section 5.3.1, IMA950-poly-ICLC vaccine will be discontinued until that toxicity has reduced to Grade 1 or less. If the vaccine cannot be reinitiated in 6 weeks, the participant will be withdrawn for the RLT.

In the pre-surgical phase:

 If the scheduled craniotomy is delayed longer than 2 weeks secondary to RLT, the patient will be withdrawn from the protocol

12 April 2020 Page 39 of 88 confidential

• If the scheduled craniotomy is delayed for reasons not related to toxicities, i.e. related to surgical scheduling issues or patient preference, patients will still be eligible if surgery is performed ≤ 35 days from randomization AND ≤ 4 days from last vaccine.

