5.3 Drug Administration

Drugs included in the current regimen are: 1) IMA950, 2) Hiltonol (poly-ICLC), and 3) varlilumab (CDX-1127). Dose vials for each of these drugs will be made under GMP conditions for administration. Refer to the IND's CMC for additional production information (The IND # TBN [name], PhD). IMA950 and poly-ICLC will be administered as one formulation containing 4.96 mg total IMA950 peptides and 1.4 mg poly-ICLC subcutaneously (s.c.) at sub-inguinal sites (IMA950-poly-ICLC vaccine). CDX-1127 will be administered intravenously (i.v.) at 3 mg/kg. Each dose must be administered at the

12 April 2020 Page 31 of 88 confidential

clinical trial site by appropriately trained staff. The rationale for doses, schedule and the selected combination are discussed in the background and rationale section (Section 2).

Each dose of vaccine must be administered at the clinical trial site by appropriately trained staff. It will be administered as one formulation containing IMA950 [413 μg of each peptide per injected dose (4.96 mg in total)] and 1.4 mg poly-ICLC subcutaneously (S.C.) at sub inguinal sites.

It is recommended that the injections be given approximately 10 cm below the inguinal ligament, within an appropriately sterilized area of 3-5 cm in diameter located over the femoral artery, on the right thigh for all injections unless an induration from the previous vaccine prevents the injection on the same site. In this case, the injection site will be altered to the corresponding area on the left thigh. The date and time of the reaction will be documented on the Vaccination Toxicity Assessment Form and patients will be called 48 \pm 6 hours after injection to assess for local reaction.

Vaccine injections should not be given to areas of skin with dermatologic conditions (such as persistent injection site reactions, infection, edema, or scarring) that will not allow easy access for study drug administration or evaluation of localized adverse events. If such conditions or other circumstances contraindicate injections as outlined above for an individual patient, alternate sites can be used, but this should be discussed with the primary investigator.

Following each administration of vaccine, patients must remain in clinic for observation one hour to evaluate and treat any potential immediate hypersensitivity reactions.

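### Section 9.1.1 counts a vaccine delay of 5 weeks or longer as an RLT while 5.6.1 sets the limit at more than 6 weeks; as a minor point, the two 5.7.1 dosing rules carry different exemptions

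*Combined protocol and SAP*

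**What the plan says.** **Delay as an RLT.** Section 5.6.1 lists among the RLTs "Dosing delays > 6 weeks for IMA950+poly-ICLC vaccines or varillumab (Arm 1 patients only) administration". The bullet gives no cause. The surgery-delay bullet beside it requires at least a possible relation to study treatment.

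Section 5.7.1 works to the same 6 weeks. On local reactions it says "If the continued inflammatory reactions at the injection site remain too severe in both legs to allow subsequent vaccines, the treatment will be suspended". That suspension may last at most 6 weeks, counted from the planned dose; failure to resolve by then is an RLT. On interruptions for adverse events it says "Delay of one vaccine (and varillumab if scheduled) administration by up to 6 weeks will not be considered a protocol violation", and then "If one or more treatment cycle is delayed by longer than 6 weeks due to an adverse event, regardless of attribution, treatment must be discontinued". Section 5.7.3 discontinues vaccination for a delay beyond 6 weeks caused by treatment-related toxicity or an RLT.

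Section 9.1.1, which defines the co-primary safety endpoint, departs from this. A vaccine dose delayed by 5 weeks or longer, whatever the reason, puts the patient off study with an RLT, even where the RLT criteria are otherwise not met. It cites those criteria as Section 5.3.1. Section 12.1.1 cites 5.3.1 as well, and 4.1 cites 5.3. Section 5.3 is Drug Administration; the definition is in 5.6.1.

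**Exemptions from withholding a dose.** In 5.7.1 the one-week delay on vaccination day applies to treatment-related effects above Grade 1, "except for grade 2 lymphopenia and injection site reactions from prior IMA950+poly-ICLC vaccine". A later sentence in the same section holds vaccination for any event at or above a "Grade 2 non-RLT AE (except grade 2 lymphopenia or flu-like symptoms), felt to be related to therapy, until they return to" Grade 1 or lower.

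**The concern.** The RLT count should not depend on which section the person coding it has read. A patient suspended under the both-legs rule who resumes in the sixth week has followed 5.7.1 exactly, with the later doses moved back to keep their intervals. Under 9.1.1 the same patient is off study with an RLT. Because 9.1.1 disregards cause, a travel or scheduling delay of 5 weeks would also be recorded as a toxicity outcome.

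The count is used in several places: the per-arm proportions with exact intervals and the Fisher comparison (12.1.1), the stopping table (12.2), and the 9.1.1 criterion that the regimen is unacceptable above 33% RLT. In an arm planned at 15 patients, one patient is 1/15, or about 6.7 percentage points of the RLT proportion.

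The 5.7.1 exemption lists are a smaller matter. Each rule names an exemption that the other takes away, so the text does not show which exemptions the sponsor means to keep.

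**Working it through.** **1. The delay limits side by side.**

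| Section | Limit | Cause stated | Consequence |
|---|---|---|---|
| 5.6.1 | more than 6 weeks | none | RLT |
| 5.7.1, both legs | not resolved in 6 weeks | injection site inflammation | RLT, withdrawn |
| 5.7.1, Grade 2 or higher, not RLT | cannot restart in 6 weeks | toxicity | withdrawn for RLT |
| 5.7.1, interruption | more than 6 weeks | adverse event, any attribution | treatment stopped |
| 5.7.3 | more than 6 weeks | treatment-related toxicity or RLT | vaccine stopped |
| 9.1.1 | 5 weeks or longer | any | off study, RLT |

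Only 9.1.1 differs on the number. The 5.7.1 interruption row and the 5.7.3 row govern stopping treatment rather than the RLT definition. They are listed because they show that 6 weeks is the working limit elsewhere.

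**2. The gap in days.** 5 weeks × 7 = 35 days and 6 weeks × 7 = 42 days. Section 9.1.1 counts delays of at least 35 days; 5.6.1 counts delays of more than 42. Days 35 to 42 inclusive, 42 − 35 + 1 = 8 whole-day values, are RLTs under 9.1.1 only. Beyond 42 days both sections count the delay. Since the 5.6.1 bullet is silent on cause, a logistical delay of that length is scored by 9.1.1 and left open by 5.6.1.

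**3. Whether one patient can matter.** The 12.2 inputs are a beta prior with α = 0.09 and β = 1.71, and a stop when the posterior probability that pRLT exceeds 0.33 is itself above 0.33.

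- Prior mean: 0.09 / (0.09 + 1.71) = 0.05. Prior probability above 0.33: 0.050. Both match the stated beliefs.
- After r RLTs in n patients the posterior is Beta(0.09 + r, 1.71 + n − r).
- The smallest r that meets the rule is 2 for n = 3–5, 3 for n = 6–9, 4 for n = 10–12 and 5 for n = 13–15. This reproduces the printed table exactly.

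Take an arm of 5 patients with one RLT from another cause and one 38-day suspension for local reactions. Under 5.6.1 the count is 1 and the trial continues. Under 9.1.1 it is 2 and the boundary is met.

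**4. The 5.7.1 exemptions side by side.**

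| Grade 2 event, related | One-week delay rule | Hold rule | Both obeyed |
|---|---|---|---|
| Lymphopenia | exempt | exempt | may be dosed |
| Injection site reaction | exempt | held | not dosed |
| Flu-like symptoms | delayed | exempt | not dosed |

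Two of the three named exemptions have no effect once both rules are applied.

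**The case against.** The strongest defence is that 9.1.1 is a deliberate safety net: it says it applies even where the RLT criteria are not met. A wider net is a legitimate choice. But 5.6.1 already contains a dosing-delay RLT with a different limit, so the plan gives two limits for one event. Correcting the 5.3.1 reference in 12.1.1 would point the analysis at 5.6.1, yet 9.1.1 would still define the endpoint differently.

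Several stronger readings are tempting, and the documents do not support them.

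- *The two 5.7.1 rules give opposite instructions.* Both are do-not-dose rules. Exemption from one is not an order to vaccinate, and taking the stricter answer satisfies both. What remains is exemptions without effect.
- *The sentence on protocol violations contradicts 9.1.1.* It does not. An RLT is an outcome, and a patient can have one without any violation.
- *Section 5.7.2 is inconsistent because it has no local-reaction exemption.* It governs the poly-ICLC dose, not timing. Reducing poly-ICLC for recurrent Grade 2 local reactions is coherent, and 5.8.2 attributes skin reactions to subcutaneous poly-ICLC.
- *The gap threatens the lead-in.* Section 4.1 watches each patient only to 6 weeks after surgery, and a toxicity-driven 5-week delay before surgery would normally already breach the 2-week surgery rule. Later delays mainly enter the 12.1.1 and 12.2 counts.

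**Conclusion.** The 5- versus 6-week conflict is real and should be corrected. It rests only on the current text of 5.6.1, 5.7.1, 5.7.3 and 9.1.1, and it affects a count used for a co-primary endpoint and a stopping rule. The 5.7.1 exemption lists are a minor drafting point.

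The size is limited to what the text fixes: delays of 35 to 42 days, plus the treatment of delays unrelated to toxicity. A reader might go further and put assumed delay rates through the 12.2 rule. At an assumed true RLT rate of 0.05, the chance that one arm reaches the boundary is 0.026. If an independent 5%, 10% or 15% of patients also had a delay scored as an RLT, the combined rate 1 − 0.95 × (1 − added rate) becomes 0.0975, 0.145 or 0.1925, and that chance becomes 0.10, 0.22 or 0.36. The documents give no rate for such delays, so these values are not an estimate for this trial. Nor do the documents support a claim that the ambiguity favours either arm.

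**What to change.** 1. **9.1.1:** replace the 5-week, any-reason clause with the 5.6.1 limit: *delayed for longer than 6 weeks*.
2. **Cause:** the sponsor should state one cause rule for a delay RLT and use it in both 5.6.1 and 9.1.1. The treatment-related wording in 5.7.3 is one option. Its downside is a slightly narrower RLT count, and so a slightly less sensitive stopping rule. That is the sponsor's safety decision.
3. **Cross-references:** change the RLT references to 5.3 and 5.3.1 (in 4.1, 5.7.1, 9.1.1 and 12.1.1) to 5.6.1.
4. **5.7.1 (minor):** use a single exemption list for the delay and the hold, with the sponsor choosing whether injection site reactions, flu-like symptoms or both stay on it.

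Section 5.7.2 needs no change. The cost is wording in one amendment, with no added patients, visits or samples.
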